#### **4.3.4. Vital Signs**

Summary statistics for vital signs and weight will be presented overall for all subjects in the SAF Population for all scheduled visits. Actual values and changes from Baseline will be summarized for all visits where collected.

#### **4.3.5. Physical Examination Findings**

A complete physical examination will be conducted at Screening and targeted physical exams will be conducted at every visit from Day 1 through Day 99 (14 weeks). Physical examination findings at each scheduled visit will be summarized overall for all subjects in the SAF Population. The number and percent of subjects with abnormal findings by body system will be tabulated.

#### **4.3.6. Medications**

[figure not shown]
All prescriptions or over-the-counter medications continued at the start of the trial or started during the trial, and different from the study drug will be recorded. All of these medications will be coded using WHO Drug Dictionary (March 2019). The use of another version will not be considered a violation of the SAP, nor require an amendment to the plan. Both the coded terms and verbatim terms will be presented in data listings for:

- Concomitant procedures (procedures are not coded)
- Previous and Concomitant medications
- ART medications – only for HIV infected subjects

### **4.4. PK**

The primary PK endpoints are to compare the AUC and trough serum drug concentration after IV Infusion with the diluted drug to the AUC and trough concentration after IV push with the undiluted drug. Serum concentrations will be used to estimate PK parameters.

PK parameters will be estimated for all subjects by non-compartmental analysis of the serum concentration-time data. Missing data will not be imputed. The AUC and trough concentrations for IV push infusions over 30 seconds and IV infusions over 15 minutes will be estimated. The following graphic illustrates the time points at which the AUC and  $C_{trough}$  values will be estimated.

A 90% confidence interval of log transform of the ratio of the geometric means for IV push to IV infusion will be calculated. A PK bridge between the IV push and IV infusion is demonstrated for AUC if the 90% confidence interval of log transform of the ratio of the geometric means for IV push (test product) to IV infusion (reference product) for the 20 subjects in the study is within a 80%-125% criteria.

In accordance with the FDA Guidance (2001) [2], SAS PROC MIXED will be used to fit a factor-analytic variance-covariance structure using the FA0(2) option to the ln-transformed AUC data by subject, population (sentinel or core), PK period, and infusion type (IVI=Reference; IVP=Test) to estimate 80%-125% criteria. For each infusion type, subject-level AUC data will be labeled as PK Period 1 or PK Period 2 corresponding to the graphic above. Unless a subject has missing data for both administration routes and both periods, the subject's data will be included in the analysis because SAS PROC MIXED can handle missing data. Details of reported outputs from the analysis will be displayed in the mock tables and will include mean estimate and its lower and upper bounds.

The following SAS code syntax will be used to calculate estimates:

```
proc mixed data=lnauc method=reml;
  class infusiontype population period ;
  model lnauc= population period infusiontype/ddf=kenwardroger;
  random infusiontype /type=FA0(2) subject=subject;
  repeated/group=infusiontype subject=subject;
  estimate 'T-R' infusiontype 1 -1/CL alpha=0.1;
  ods output estimates=test;
  data test;
  set test;
  meanrat= exp (estimate); * Estimated mean ratio on original scale;
  lowerb=exp(lower); * Lower bound on original scale;
  upperb=exp(upper); * Upper bound on original scale;
  proc print data=test noobs;
  var meanrat lowerb upperb;
  run;
```

The  $C_{trough}$  values for all IV push and all IV infusions over 15 minutes will be estimated. Additionally, the PK bridge will be demonstrated if the proportion of subjects with average  $C_{trough}$  equal to or exceeding the threshold of 300 ng/mL are comparable for IV infusion over 15 minutes to IV push over 30 seconds. Analysis will be conducted by pooling all the  $C_{trough}$  measurements into two groups (IVI=Reference; IVP=Test) and dichotomizing the  $C_{trough}$  data ( $< 300$  ng/mL=1;  $\geq 300$  ng/mL=0). Fisher's exact test for comparing two independent binomial proportions will be conducted initially to test for equality of the proportions. In a subsequent test, the PK bridge will be based on relative risk assuming that the binary data in the two infusion groups are independent samples. Two one-sided tests of significance (TOST) will be carried out for the pair of hypotheses,  $H_{0a}: \rho \leq \rho_0$  versus  $H_{1a}: \rho > \rho_0$  and  $H_{0b}: \rho \geq \rho_1$  versus  $H_{1b}: \rho < \rho_1$ . Rejection of both  $H_{0a}$  and  $H_{0b}$  would mean that the relative risk lies in the zone of equivalence. The syntax below will be used in SAS to carry out the score test with  $\rho_0 = 0.8$ , and  $\rho_1 = 1.25$ .

```
proc freq data=<filename> order=data;
  tables group*Ctrough/relrisk(equivalence margin=(.80, 1.25)
  method=FM);
  weight count;
  format Ctrough Ctrough. ;
  run;
```

Details of reported outputs from the analysis will be displayed in the mock tables and will include relative risk, equivalence limits, 90% confidence limits, and TOST p-values of lower margin, upper margin, and overall. Missing data will not be imputed or used in the analysis. In addition, the two-tailed p-value from Fisher's exact test will be presented to provide additional supporting evidence for equality of binomial proportions between the two administrative routes in the  $C_{trough}$  cutoff at 300 ng/mL.

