**Table 14.2.1**  
**90% Confidence Interval of the LOG Transform of the Ratio of the**  
**Geometric Means of AUC For 30 Second IV Push to 15 Minute IV Infusion**  
**Intent-to-Treat Population (Sentinel and Core Subjects Pooled)**

Analysis Type	Results
Type 3 Tests of Fixed Effects	
PK Period	
F Value	xxxx
Pr > F	xxxx
Administration Route	
F Value	xxxx
Pr > F	xxxx
Group (Sentinel or Core)	
F Value	xxxx
Pr > F	xxxx
Estimates (30 Second IV Push/15 Minute IV Infusion)	
Estimate (Standard Error)	xxxx (xxxx)
t Value (df)	xxxx (xx)
Pf >  t	xxxx
90% Confidence Interval	(xxxxx, xxxx)
Back Transformed Estimates	
Mean Geometric Ratio	xxxx
90% Confidence Interval [1]	(xxxxx, xxxx)

[1] A pharmacokinetic bridge between the IV push and IV infusion is demonstrated for AUC if the 90% confidence interval of log transform of the ratio of the geometric means for IV Push (test product) to IV infusion (reference product) for the enrolled subjects in the study is within an 80%-125% criteria.

**Note to Programmer:** SAS code provided in SAP. Any subject with at least some non-missing PK data is included.

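### In the IV push SAP, the AUC contrast labelled 'T-R' computes infusion minus push under the SAP's own level names, so the reported ratio and 90% CI are inverted

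*SAP*

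**What the plan says.** The IV push SAP, Section 4.4 (PK), fixes the direction of the AUC comparison in words: the bridge rests on the "ratio of the geometric means for IV push (test product) to IV infusion (reference product) for the 20 subjects in the study". It assigns the roles as "infusion type (IVI=Reference; IVP=Test) to estimate 80%-125% criteria".

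The SAS code it says will be used has these parts:

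- The procedure call is "proc mixed data=lnauc method=reml", with no `ORDER=` option.
- The CLASS statement is "class infusiontype population period", with no reference level or reordering.
- The contrast is "estimate 'T-R' infusiontype 1 -1/CL alpha=0.1".
- The back-transformation is "meanrat= exp (estimate); * Estimated mean ratio on original scale", with no change of sign. The limits are exponentiated in the same way.

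Mock Table 14.2.1 of the IV push tables heads the result rows "Estimates (30 Second IV Push/15 Minute IV Infusion" and sends the programmer to the SAP for the code.

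The IM SAP, Section 4.5 (PK), has the same ESTIMATE line, with IVI as reference and IM as test.

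**The concern.** An ESTIMATE statement applies its coefficients to the CLASS levels in the order in which the procedure holds them. With no `ORDER=` option, PROC MIXED sorts levels in ascending order of formatted value. The label 'T-R' is only text and does not affect which level receives +1. If the reference level sorts first, the output is R-T printed under a T-R label.

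Comparing AUC after push with AUC after infusion is a primary objective (Protocol Section 2.1; IV push SAP Section 2.2.1). An inverted contrast would give the wrong direction for the log estimate, the t value, the geometric mean ratio and both confidence limits. A reader of Table 14.2.1 would be told that push raises exposure when it lowers it, or the reverse. If the bridge failed, the failure would appear at the wrong limit.

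**Working it through.** The plan states no numerical result that depends on this contrast, so there is no figure to reproduce. The one numeric setting, alpha=0.1, does give the stated 90% interval.

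**Step 1: level order and contrast.** Sort each pair of labels in ascending order and apply +1 to the first and -1 to the second.

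| Labels | Where they come from | Sorted order | `1 -1` gives |
|---|---|---|---|
| IVI, IVP | IV push SAP 4.4 | IVI, IVP | R - T (inverted) |
| Reference, Test (or R, T) | role names in 4.4 | Reference, Test | R - T (inverted) |
| 15 Minute IV Infusion, 30 Second IV Push | mock Table 14.2.1 | infusion, push | R - T (inverted) |
| Inf 15m, Push 30s | Listing 16.2.4.1 (IV push) | infusion, push | R - T (inverted) |
| IM, IVI | IM SAP 4.5 | IM, IVI | T - R (correct) |

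The line is therefore right in the IM SAP under its own labels, but only because IM sorts before IVI. It would reverse there too if the data were coded R/T.

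**Step 2: what is printed.** Let d = ln(push/infusion), with 90% limits d ± h. The code returns -d with limits -d ± h. After exponentiation the ratio is 1/exp(d), and the limits are 1/exp(d + h) and 1/exp(d - h): the reciprocals of the correct limits, swapped. The standard error, the two-sided p-value and the Type 3 F tests do not change. The signs of the estimate and t value do.

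**Step 3: the decision.** The bridge requires -ln 1.25 ≤ d - h and d + h ≤ ln 1.25, because ln 0.80 = -0.2231 = -ln 1.25. Replacing d by -d only exchanges the two conditions, so pass or fail is the same in both directions. A check on 200,000 simulated intervals found no disagreement.

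**Step 4: size, by illustration.** The true ratios are assumptions. Precision uses the within-subject CVs of AUC in Protocol Section 9.8: median 7%, and maximum 22% to 23%, taken here as 22.5%. Those CVs are for IM and infusion, and I assume that they carry over to push. With 20 subjects and two AUC periods per route, and ignoring subject-by-route interaction:

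- s = sqrt(ln(1 + CV²)), which is 0.0699 at 7% and 0.2222 at 22.5%.
- The variance of a subject's mean difference is 2 × s²/2 = s², so SE = s/√20, which is 0.0156 and 0.0497.
- h = t(0.95, 19 df) × SE = 1.729 × SE, which is 0.0270 and 0.0859.

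| CV | Assumed push/infusion | Correct ratio (90% CI) | As coded (90% CI) | Within 0.80-1.25, both directions |
|---|---|---|---|---|
| 7% | 0.85 | 0.850 (0.827, 0.873) | 1.176 (1.145, 1.209) | yes |
| 7% | 0.90 | 0.900 (0.876, 0.925) | 1.111 (1.081, 1.142) | yes |
| 7% | 1.10 | 1.100 (1.071, 1.130) | 0.909 (0.885, 0.934) | yes |
| 22.5% | 0.85 | 0.850 (0.780, 0.926) | 1.176 (1.080, 1.282) | no |
| 22.5% | 0.90 | 0.900 (0.826, 0.981) | 1.111 (1.020, 1.211) | yes |
| 22.5% | 1.10 | 1.100 (1.009, 1.199) | 0.909 (0.834, 0.991) | yes |

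At a true ratio of exactly 1 the point estimate does not change, and the misreport grows with distance from 1. In the row that fails, the true failure is at the lower limit (0.780 < 0.80), but the output would show it at the upper limit (1.282 > 1.25).

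**The case against.** The strongest reply is that the SAP does not specify the stored values of `infusiontype`. IVI and IVP are given as roles, and a numeric code or format that put push first would make the line correct. Mixed-style labels could do so by accident: IV Push sorts ahead of IVI, because a blank precedes a letter. That is true, and the finding is conditional on the level names. But the levels that Section 4.4 names invert the ratio, as do the other IV push SAP label pairs checked above, and nothing in the SAP directs the programmer to any other order. Order is set for the trough analysis in the same section, where the PROC FREQ call uses `order=data`, but not for the AUC model.

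A second reply is that the code would be edited before use anyway: it has `ddf=` where PROC MIXED takes the Kenward-Roger method through `ddfm=`. Correcting that option leaves the contrast as it is.

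Third, the intended direction is plain from the text and the mock table, the table shells require quality-control checks, and AUC is listed by subject, so a reversal could be detected. It could be, but no stated check covers level order, and output labelled 'T-R' in a push/infusion row gives no warning.

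Two limits stand in full. The bridge decision is unaffected. The 0.90 example is an assumption: at CV 7% its interval is much tighter than at the maximum CV, and no document predicts a 10% difference.

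**Conclusion.** The concern holds. With the levels IVI and IVP and default CLASS ordering, the IV push code returns infusion/push in a table that says push/infusion. The error replaces the ratio by its reciprocal, swaps the confidence limits, and reverses the sign of the log estimate and t value. For an assumed true ratio of 0.90, the report would show 1.11. Type I error, power and the 80%-125% verdict do not change.

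The conclusion rests on two assumptions: that the dataset uses the SAP's names or others that put infusion first, and that no order option is added. The IM SAP line is correct under the labels IM and IVI and is not itself an error. It depends on label spelling in the same way.

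**What to change.** In the IV push SAP, Section 4.4, change the contrast to `infusiontype -1 1`. Alternatively, set the order of `infusiontype` explicitly so that the test route comes first, and keep the coefficients. State the level order in the IM SAP as well, so that its line no longer depends on how the labels sort.

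Add a programming check that the exponentiated estimate agrees in direction with the test/reference ratio of the raw geometric means. Exact equality should not be required, because the model-based estimate can differ from the raw ratio when AUC data are missing. If Table 14.2.1 has already been produced, check its direction against the listed AUC values.

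The cost is one line of code and one check. No data collection, sample size or decision rule changes.

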#### 4.5. Secondary Efficacy Endpoint

Assessment of the HIV-1 viral load measurements in HIV-1 infected subjects will be made as a secondary endpoint by comparing the mean viral load (log10 and copies/ml) at all visits when subjects received an approved IV infusion over 15 minutes to the visits when receiving an IV push over 30 seconds. Note: Prior to calculating change from Baseline in viral load, the log10 value of each measurement will be calculated and will be rounded to one decimal point.

Study subjects will be considered virologic failures if:

1. Viremic subjects experience a sustained >0.5 log increase in plasma HIV-1 RNA from Baseline

or

2. A sustained viral load >200 copies/mL if subject viral load was <50 copies/mL at Baseline

that cannot be explained by intercurrent illness, a change in adherence to the background regimen, or unanticipated changes to the background regimen. Note: Sustained is defined as two consecutive viral load determinations at least 2 weeks apart.

The proportion of subjects who experienced virologic failure at any time during the study will be summarized.

#### ***4.6. Graphical Displays***

In addition to the tables and listings described above, the following graphical displays will also be included for in HIV-1 infected subjects:

- Mean (+/- Standard Error [SE]) viral load levels (copies/mL) at all scheduled visits;
- Mean (+/- SE) change from Baseline in viral load levels (copies/mL) at all scheduled visits;
- Mean (+/- SE) CD4+ cell count (cells/mm^3) at all scheduled visits; and
- Mean (+/- SE) change from Baseline in CD4+ T-cell count (cells/mm^3) at all scheduled visits.

#### ***4.7. Exploratory/Other Analyses***

Exploratory statistical analyses will examine any noted changes in HIV-1 drug sensitivity/susceptibility in participants with an increase in plasma viral load to levels above 1,000 copies/mL on two consecutive measurements at least 2 weeks apart. These reports will be prepared separately from the report prepared in accordance with the rest of this SAP.

[figure not shown]

## **Appendix 1**

### **Analysis Phases, Periods, and Subperiods**

[figure not shown]
**Sentinel Group (ARM="SENTINEL")**

**Core HIV-infected Group (ARM="CORE")**

**Core HIV-uninfected Group (ARM="CORE UNINFECTED")**

\*The first infusion during this period is 2000mg over 60 mins but all other infusions during this period are 800mg over 15 mins.

**Notes Applicable to All Listings**

General Programming Notes:

1. There are a few listings that might fit as they are or might have to be split once we see the output with actual data.
2. All listings should start with and be sorted by Group (Sentinel or Core), Subject ID (concatenation of site number and Subject number), and visit date as appropriate.
3. If columns with specific text should be widened due to the amount of text, it is up to the programmer's discretion. However, please keep to the industry standard margin of 1 inch on bottom and sides and 1.25 inches on the top. Font is Courier New 8 point.
4. For all dates used, character format dates to capture partial dates. Use dashes where a month or day is missing. If entire date is missing just leave blank. i.e., - JAN2011 or 01-2011.
5. If a programming note appears on the mock listing indicating that the footnote should appear only on the first page, this means the first page of output contains all footnotes and ONLY footnotes. All subsequent pages contain data with one footnote that says "Refer to page 1 for footnotes".
6. Some of the mock tables display numbers rather than x's. The numbers are meaningless and are for example only. Where visit names are displayed in tables, these are examples as well. Correct visit names for the TMB-302 study should be displayed in the actual output.
7. Each listing should include all applicable data, even if only a subset of the full set of treatment groups is displayed in the mocks.
8. Sort each listing by Group and then Subject ID where applicable.
9. Add "Period" to any applicable listing as the data dictates. Some listings below have period added with example values.

**Listing 16.2.1.1  
Subject Disposition**

---

Group	Subject ID	Screened	ITT Population [1]	SAF Population [2]
Sentinel	302-XX-XXX	YES	YES	YES
	302-XX-XXX	YES	YES	YES
Core HIV-infected	302-XX-XXX	YES	YES	YES
	302-XX-XXX	YES	YES	YES
Core HIV-uninfected	302-XX-XXX	YES	YES	YES
	302-XX-XXX	YES	YES	YES

[1] Intent-to-Treat (ITT) Population consists of all Subjects enrolled into the study.

[2] Safety (SAF) Population consists of Subjects receiving at least one partial dose of study drug.

**Listing 16.2.1.2  
Discontinuation**

Group	Subject ID	Study Discontinuation Date	Date of Last Study Treatment	Completed Study Treatment	Reason for Treatment Discontinuation	Completed Study	Reason for Study Discontinuation	Death Date

**Listing 16.2.2.1**  
**Text of Inclusion and Exclusion Criteria**

Criterion Type	Criterion Number	Criterion Text [1]
Inclusion	1	XX
	2	XX
	...	
	8	
Exclusion	1	XX
	2	XX
	...	
	10	

[1] Full detailed text:

Westat (Created on DDMMYYYY)  
S:\TMB302\DA\SAS\L\_INCEXL.SAS

**Listing 16.2.2.2  
Protocol Violations**

Group	Subject ID	Visit	Start Date	Stop Date	Violation Code	Details of Violation	Approval Obtained	Date of Approval
Sentinel	302-XX-XXX	XXXXXX	YYYY-MM-DD	YYYY-MM-DD	XXX	XXXXXXXXXXXX	Yes/No	YYYY-MM-DD
Core HIV-infected	302-XX-XXX	XXXXXX	YYYY-MM-DD	YYYY-MM-DD	XXX	XXXXXXXXXXXX	Yes/No	YYYY-MM-DD
Core HIV-uninfected	302-XX-XXX	XXXXXX	YYYY-MM-DD	YYYY-MM-DD	XXX	XXXXXXXXXXXX	Yes/No	YYYY-MM-DD

Westat (Created on DDMMMYYYY)  
S:\TMB302\DA\SAS\L\_PROTVIOS.SAS

**Listing 16.2.2.3  
Protocol Deviations**

Group	Subject ID	Visit	Start Date	Stop Date	Deviation Code	Details of Deviation	Approval Obtained	Date of Approval
Sentinel	302-XX-XXX	XXXXXX	YYYY-MM-DD	YYYY-MM-DD	XXX	XXXXXXXXXX	Yes/No	YYYY-MM-DD
Core HIV-infected	302-XX-XXX	XXXXXX	YYYY-MM-DD	YYYY-MM-DD	XXX	XXXXXXXXXX	Yes/No	YYYY-MM-DD
Core HIV-uninfected	302-XX-XXX	XXXXXX	YYYY-MM-DD	YYYY-MM-DD	XXX	XXXXXXXXXX	Yes/No	YYYY-MM-DD

Westat (Created on DDMMYYYY)  
S:\TMB302\DA\SAS\L\_PROTDEV.SAS

**Listing 16.2.2.4**  
**Inclusion/Exclusion Criteria Violations/Deviations**

Group	Subject ID	Date of Informed Consent	Time of Informed Consent (hh:mm)	Will this Subject be Enrolled	Criterion Type and Number [1]
Sentinel	302-XX-XXX	YYYY-MM-DD	XX:XX	Yes/No	EXC XXX/INC XXX
Core HIV-infected	302-XX-XXX	YYYY-MM-DD	XX:XX	Yes/No	EXC XXX/INC XXX
Core HIV-uninfected	302-XX-XXX	YYYY-MM-DD	XX:XX	Yes/No	EXC XXX/INC XXX

[1] Refer to Listing 16.2.2.1 for text.

Westat (Created on DDMMYYYY)  
S:\TMB302\DA\SAS\L\_INCEXLVIOS.SAS

**Listing 16.2.3.2**  
**Medical History**

Group	Subject ID	Medical Condition/Surgery	Start Date	Stop Date	CDC AIDS-Defining Condition
Sentinel	302-XX-XXX	XXXXXXXXXXXXXX	YYYY-MM-DD	YYYY-MM-DD or ONGOING	NO
Core HIV-infected	302-XX-XXX	XXXXXXXXXXXXXX	YYYY-MM-DD	YYYY-MM-DD or ONGOING	YES
Core HIV-uninfected	302-XX-XXX	XXXXXXXXXXXXXX	YYYY-MM-DD	YYYY-MM-DD or ONGOING	YES

Westat (Created on DDMMYYYY)  
S:\TMB302\DA\SAS\L\_MEDHIST.SAS

**Listing 16.2.4.1**  
**Study Drug Administration**

Group	Subject ID	Visit	Visit Date	Method of Administration [1]	Start Time (hh:mm:ss)	Stop Time (hh:mm:ss)	Administration Site	Infusion Side	Starting Volume (mL)	Ending Volume (mL)	Entire Dose Delivered	Reason if No or Interrupted
Sentinel	302-XX-XXX	XXXXXXX	YYYY-MM-DD	Inf 15m	XX.XX:XX	XX.XX:XX	Cephalic Vein	Left	XXX	XXX	Yes	XXXXXXXXXX
		XXXXXXX	YYYY-MM-DD	Inf 10m	XX.XX:XX	XX.XX:XX	Other Vein: specify	Right			No	
Core HIV-infected	302-XX-XXX	XXXXXXX	YYYY-MM-DD	Bolus 1m	XX.XX:XX	XX.XX:XX	Cephalic Vein	Left	XXX	XXX	Yes w/ Interruption	XXXXXXXXXX
Core HIV-uninfected	302-XX-XXX	XXXXXXX	YYYY-MM-DD	Bolus 1m	XX.XX:XX	XX.XX:XX	Cephalic Vein	Left	XXX	XXX	Yes w/ Interruption	XXXXXXXXXX

[1] Method of Administration: Inf 15m = IV Infusion 15 minutes, Inf 10m = IV Infusion 10 minutes, Bolus 5m = IV Bolus 5 minutes,  
Bolus 1m = IV Bolus 1 minute, Push 30s = IV Push 30 seconds

Westat (Created on DDMMYYYY)  
S:\TMB302\DA\SAS\L\_DRUGAMIN.SAS

**Listing 16.2.4.2**  
**ART Exposure [1]**

Group	Subject ID	Medication	Standardized Medication									
			Name [2]	Indication	Start Date	Stop Date	Period[3]	Dose	Unit	Route	Frequency	
Sentinel	302-XX-XXX	XXXXXXXX	XXXXXXXX	XXXXXXXX	YYYY-MM-DD	YYYY-MM-DD Or ONGOING	Inf 15m/ Inf 10m/	XXXX	XXXX	XXXX	XX	
Core HIV-infected	302-XX-XXX	XXXXXXXX	XXXXXXXX	XXXXXXXX	YYYY-MM-DD	YYYY-MM-DD Or ONGOING	Bolus 5m/ Bolus 1m/ Push 30s/ Screening	XXXX	XXXX	XXXX	XX	
Core HIV-uninfected	302-XX-XXX	XXXXXXXX	XXXXXXXX	XXXXXXXX	YYYY-MM-DD	YYYY-MM-DD Or ONGOING	Bolus 5m/ Bolus 1m/ Push 30s/ Screening	XXXX	XXXX	XXXX	XX	

[1] ART medications beginning from 3 months prior to Screening visit.

[2] Medications were coded with WHO Drug Dictionary Version March, 2019.

[3] Period represents the timeframe when the medication was STARTED.

Westat (Created on DDMMYYYY)  
S:\TMB302\DA\SAS\L\_ARTEXP.SAS

